48.0	1	99	6
48.4	85	15	6
60.0	85	15	6
Condition II (Hydrophilic Substances)			
Mobile phase A		Mobile phase B	
0.1% Formic acid in 99.9% ddH ₂ O		0.1% Formic acid in 99.9% MeOH	
Time (min)	%A	%B	Curve
0	95	5	6
14	30	70	6
16	30	70	6
18	50	50	6
MS conditions			
Detector	Waters ACQUITY QDa (Performance)		
Ionization mode	ESI Negative (I); ESI Negative and Positive (II)		
Capillary voltage	Default (0.8 kV)		
Probe temp	Default (600°C)		
Cone voltage	20V(I); 15V(II)		
Sampling rate	8 Hz		
Full scan	250-600 m/z for Negative (I); 70-600 m/z for Negative or Positive		
SIR	See Table 2 - "Molecular Ions (m/z)"		

e. Method validation :

Including Limits of detection, LOD and Limits of quantitation, LOQ, Calibration curve, Recovery, accuracy and precision, Intra-assay, accuracy and precision and Inter-assay precision and accuracy of each test substance.

Table 2. LC-MS analysis Standard List:

	Molecular ion (m/z)	Ion source mode

Lipophilic Substances			
Short Chain Fatty acids (SCFAs)	Acetate (2:0)	42.0+153 (3NPH)	ESI Negative
	Propionate (3:0)	57+153 (3NPH)	ESI Negative
	Butyrate (4:0)	72+153 (3NPH)	ESI Negative
Long Chain Fatty acids	Palmitic acid, PA (16:0)	255.1	ESI Negative
	Stearic Acid, SA (18:0)	283.2	ESI Negative
	Palmitoleic Acid, POA (16:1)	253.2	ESI Negative
	Oleic Acid, OA (18:1)	281.2	ESI Negative
Fatty acid esters of hydroxy fatty acids (FAHFAs)	Palmitoleic Acid Ester of 9-Hydroxystearic Acid (9-POHSA)	535.5	ESI Negative
	Oleic Acid Ester of 9-Hydroxystearic Acid (9-OAHSA)	563.5	ESI Negative
Internal standards			
	[¹³ C ₁₆]- Palmitic acid (IS1)	271.4	ESI Negative
Hydrophilic Substances			
Methionine cycle	L -Methionine (L -Met)	150.1	ESI Positive
	S -adenosyl- L -methionine (SAM)	399.0	ESI Positive
	S -adenosyl- L -homocysteine (SAH)	385.0	ESI Positive
	L -Homocysteine (L -Hcy)	136.1	ESI Positive
	Methylmalonic acid (MMA)	117.1	ESI Negative
Antioxidants	Ascorbic acid (AA)	174.9	ESI Negative
Nutrition index	3-Methyl- L -histidine (3-MH)	170.0	ESI Negative
Fatty acids carrier	L -Carnitine (L -Car)	162.1	ESI Positive
	Acetyl- L -Carnitine (ALC)	204.0	ESI Positive
	Propionyl- L -Carnitine (PLC)	218.0	ESI Positive
Nephrotoxin	Trimethylamine N -oxide (TMAO)	76.0	ESI Positive
	Indoxyl Sulfate (InS)	211.9	ESI Negative
	p -Cresyl sulfate (pCS)	187.0	ESI Negative
Internal standards			

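### Table 2 pairs 3-methyl-L-histidine with a positive-mode mass and negative polarity, so its selected-ion channel as written would not usefully quantify it (minor)

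*Protocol*

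**What the plan says.** All of this stands in Protocol section H, item 6 (Stool and Blood LC-MS Analysis).

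- Table 2, hydrophilic substances, nutrition index: "3-MH) 170.0 ESI Negative". This is the only analyte under that label.
- Table 1, MS conditions, gives the SIR channels by reference: "See Table 2 - 'Molecular Ions". Table 2 therefore serves as the acquisition setting.
- Table 1 gives the ionisation mode as "ESI Negative (I); ESI Negative and Positive (II". Condition II is the one for hydrophilic substances, so both polarities are available for 3-MH.
- Table 1 names the detector as "Waters ACQUITY QDa (Performance" and lists, besides SIR, a full scan over 70-600 m/z in negative or positive mode.
- Neighbouring rows of Table 2 show the pattern that the table follows: "pCS) 187.0 ESI Negative" and "Ascorbic acid (AA) 174.9 ESI Negative" in negative mode, "ALC) 204.0 ESI Positive" in positive mode.
- Sub-section e plans detection and quantitation limits, a calibration curve, recovery, accuracy and precision for each test substance.

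**The concern.** In electrospray a small molecule normally appears one proton heavier in positive mode and one proton lighter in negative mode. Mass and polarity in a table row must therefore agree. For 3-MH they do not: the mass is that of the positive ion and the polarity is negative.

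Because Table 1 draws its SIR channels from Table 2, an instrument set up from the protocol would monitor m/z 170.0 in negative mode, about 1.9 units above the 3-MH anion. A signal there would come mostly from background or another compound. If nobody noticed, it could be tabulated as 3-MH. An assay channel is fixed in the protocol and is not something that one would expect a statistical analysis plan to supply.

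**Working it through.** **Inputs.** From the protocol: the m/z and polarity of each Table 2 row. From outside the protocol, as assumptions: elemental formulas, monoisotopic atomic masses (C 12.000000, H 1.007825, N 14.003074, O 15.994915), proton mass 1.007276, natural isotope abundances, singly charged ions, and a detector of about unit mass resolution.

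**Formulas.** Positive ion = M + 1.007; negative ion = M - 1.007.

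**3-MH, C7H11N3O2.**

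M = 7(12.000000) + 11(1.007825) + 3(14.003074) + 2(15.994915) = 84.000 + 11.086 + 42.009 + 31.990 = 169.085

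- Positive: 169.085 + 1.007 = 170.092. Table 2 minus this: 170.0 - 170.092 = -0.09.
- Negative: 169.085 - 1.007 = 168.078. Table 2 minus this: 170.0 - 168.078 = +1.92.

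The listed 170.0 is therefore not reproduced in the stated polarity, but it is in the opposite one.

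**Does the rest of the table follow the rule?** The same calculation for every underivatised row, in its stated polarity (differences taken before rounding):

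| Substance | Formula | Mode | Calculated | Table 2 | Difference |
|---|---|---|---|---|---|
| Palmitic acid | C16H32O2 | - | 255.233 | 255.1 | -0.13 |
| Stearic acid | C18H36O2 | - | 283.264 | 283.2 | -0.06 |
| Palmitoleic acid | C16H30O2 | - | 253.217 | 253.2 | -0.02 |
| Oleic acid | C18H34O2 | - | 281.249 | 281.2 | -0.05 |
| 9-POHSA | C34H64O4 | - | 535.473 | 535.5 | +0.03 |
| 9-OAHSA | C36H68O4 | - | 563.504 | 563.5 | 0.00 |
| 13C16-palmitic acid (IS1) | 13C16H32O2 | - | 271.287 | 271.4 | +0.11 |
| Methionine | C5H11NO2S | + | 150.058 | 150.1 | +0.04 |
| SAM | C15H22N6O5S | + | 399.145 | 399.0 | -0.14 |
| SAH | C14H20N6O5S | + | 385.129 | 385.0 | -0.13 |
| Homocysteine | C4H9NO2S | + | 136.043 | 136.1 | +0.06 |
| Methylmalonic acid | C4H6O4 | - | 117.019 | 117.1 | +0.08 |
| Ascorbic acid | C6H8O6 | - | 175.025 | 174.9 | -0.12 |
| **3-MH** | C7H11N3O2 | - | **168.078** | **170.0** | **+1.92** |
| Carnitine | C7H15NO3 | + | 162.112 | 162.1 | -0.01 |
| Acetylcarnitine | C9H17NO4 | + | 204.123 | 204.0 | -0.12 |
| Propionylcarnitine | C10H19NO4 | + | 218.139 | 218.0 | -0.14 |
| TMAO | C3H9NO | + | 76.076 | 76.0 | -0.08 |
| Indoxyl sulfate | C8H7NO4S | - | 212.002 | 211.9 | -0.10 |
| p-Cresyl sulfate | C7H8O4S | - | 187.007 | 187.0 | -0.01 |
| d3-Methionine (IS2) | C5H8D3NO2S | + | 153.077 | 153.1 | +0.02 |
| d9-TMAO (IS3) | C3D9NO | + | 85.132 | 85.0 | -0.13 |

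That is 19 analytes and 3 internal standards. The other 21 rows agree within 0.15; 3-MH is off by 1.92, more than ten times as far as any of them. Rounding does not explain a gap of that size. The three short-chain fatty acid rows are written as sums with a derivatising agent and are left out of this check.

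**Could another negative ion give 170?** Common adducts do not: formate gives 214.1 and chloride 204.1. The protocol states no derivatisation for 3-MH.

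**What would the channel see?** Only the second isotope peak (M+2) of the negative ion falls near 170. Relative to the main peak of C7H10N3O2, with isotope ratios C 0.0107/0.9893 = 0.01082, N 0.00364/0.99636 = 0.00365 and 18-O 0.00205/0.99757 = 0.00205:

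21(0.01082)² + 3(0.00365)² + 21(0.01082)(0.00365) + 2(0.00205) = 0.0025 + 0.0000 + 0.0008 + 0.0041 = 0.0074, or about 0.7%.

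**Scale.** Table 2 has 9 lipophilic and 13 hydrophilic analytes, 22 in all; 3-MH is one. LC-MS samples are taken before treatment and after month 1 (section H, item 2), so at most 150 x 2 = 300 subject-visits.

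**The case against.** Four points can be made against giving this weight.

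- **The protocol has its own safeguards.** Sub-section e requires a calibration curve and detection limits for each substance. A 3-MH standard read where only about 0.7% of its negative-ion signal falls would probably fail to calibrate. Table 1 also lists a full scan over 70-600 m/z, which covers both 168 and 170. This stands, and it limits the consequence.
- **It may be one wrong word.** The mass fits ESI Positive, a mode that Condition II already runs, so the laboratory's actual method may be right. This is plausible but cannot be confirmed from the document. It explains the error without removing it from a table that Table 1 uses as a setting.
- **Nothing in the trial's conclusions depends on it.** Item 8 compares questionnaire improvement percentages, item 9 rests on symptom response, and the Background in section G does not name 3-MH among the metabolites of interest. This stands.
- **The formula is not in the protocol.** True, and it is labelled above as an outside input. It follows from the named compound, and the same approach reproduces the 21 other rows.

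A reader might infer that 3-MH will go unmeasured and that all 300 values will be uninterpretable. The documents do not support that. It would follow only if the validation failed to expose the channel or were not done, and the full scan were not used either. Nor is the loss of all nutrition-index data a measure of size, since that label covers this single row.

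**Conclusion.** The row is wrong as written. Its mass belongs to positive mode, its polarity is negative, and it is the only underivatised row in Table 2 where the two disagree. Since Table 1 takes the SIR channels from this table, the 3-MH channel as specified would not usefully quantify the analyte.

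The conclusion rests on the standard formula for 3-MH, singly charged protonated or deprotonated ions, and roughly unit mass resolution. The protocol states none of these, but agreement within 0.15 in the other 21 rows supports using them.

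Severity is minor. The exposure is one exploratory analyte out of 22, and the planned validation or the full scan may catch or recover it. No efficacy comparison, significance test or sample-size figure changes.

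**What to change.** Reconcile the 3-MH row of Table 2 in one of two ways: m/z 170.1 with ESI Positive, or m/z 168.1 with ESI Negative. The laboratory should choose according to the method it actually intends to run. Then carry out the 3-MH validation already planned in sub-section e on the corrected channel, before any subject sample is analysed.

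The cost is an edit to one table row. Condition II already acquires both polarities and the validation is already planned, so no extra sample or run is needed.

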3. Medicine expenses (Jingsi herbal drink concentrate, please fill in the quantity)	Jingsi herbal drink concentrate (2 packs*30 days*150 people)	0	9,000	0
	Placebo (2 packs*30 days*150 people)	0	9,000	0
	Subtotal			0
4. Subject subsidy	Subject allowance (subsidy)	1,200	150	180,000
	Subtotal			180,000
5. Inspection fee (Please fill in the inspection items and fees)	LC-MS sample processing and analysis, intestinal bacteria analysis	5,000	150	750,000
	Subtotal			750,000
total				1,450,000

E. Summary of the plan in Chinese

Please give an overview of the main points of this project within 500 words, and customize keywords according to the nature of this project, and please write in Chinese.

新冠肺炎患者在痊癒後，約 10% 患者產生長新冠症狀，長新冠症狀中的腹痛、腹脹、腹瀉及便秘源自於腸腦軸失調，腸腦軸失調包含功能性消化不良和腸躁症，常規檢查無明顯異常，由於原因不明但盛行率高，往往對患者的身心健康影響甚鉅。即使腸腦軸失調目前被認為和胃腸道局部發炎和微生物菌相改變有關，但目前西醫治療療效不佳。有鑑於此，許多研究應用中草藥在功能性消化不良，並且達到不錯的療效。淨斯本草飲濃縮液為取得衛福部外銷專用許可證之食品，其成分為艾葉、魚針草、麥門冬、魚腥草、桔梗、甘草、紫蘇葉、菊花等臺灣本土八種能清潤、散寒、宣肺化痰、利濕清熱的中藥草，在臨床試驗登記立案作為輔助新冠肺炎的治療，目前初步發現亦可改善患者腸胃症狀以及憂慮程度。故本研究採雙盲隨機試驗，以淨斯本草飲濃縮液用於客觀檢查皆正常之長新冠症狀-腸腦軸失調患者，評估其治療前後之身心症狀以及腸道菌代謝產物之變化。

關鍵詞：長新冠症狀、腸腦軸失調、淨斯本草飲濃縮液、身心症狀

計畫概述：請概述執行本計畫之目的及可能產生對社會、經濟、學術發展等面向的預期影響性(三百字以內)。

腸腦軸失調(DGBI)包含功能性消化不良和腸躁症為新冠肺炎感染後的腸胃道問題，也是傳統西醫療效值得改善的疾病，淨斯本草飲濃縮液為東部地區研發之中草藥食品，期待淨斯本草飲濃縮液在感染新冠肺炎病毒後改善腸胃道功能以及憂鬱情況的發現能夠用於改善腸腦軸失調(DGBI)之身心症狀。

※此部分內容於獲核定補助後將逕予公開

F. Summary of the plan in English

Please provide an overview of the main points of this project within 500 words, and customize keywords according to the nature of this project, and please write in English.

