pneumonia will be recruited in the outpatient department of gastroenterology, including 75 subjects with functional dyspepsia (FD) and 75 subjects with irritable bowel syndrome (IBS) subjects; qualified subjects will receive blood and feces sampling and complete physical and mental symptom assessment (sleep habits questionnaire, anxiety questionnaire, stress questionnaire, gastrointestinal symptoms questionnaire, and irritable bowel syndrome questionnaire) before treatment, and then according to the double-blind random allocation method, the computer generated garbled characters, and assigned Jing Si Herbal Tea Liquid Packet or placebo according to the coding sequence, and the research assistant gave Jing Si Herbal Tea Liquid Packet or placebo, Host and recipients None of the subjects knew what the content of the assignment was. The experimenters took Jing Si Herbal Tea Liquid Packet or placebo in the first month, and after the end of the month, they received blood and stool tests and complete physical and mental symptom assessment (sleep habits questionnaire, anxiety questionnaire, stress questionnaire), gastrointestinal symptom questionnaire, and irritable bowel syndrome questionnaire), the laboratory will conduct pre- and post-test analysis of LC-MS and intestinal bacteria, and then conduct a cross-test. The original placebo will take Jing Si Herbal Tea Liquid Packet in the second month, previously taking Jing Si Herbal Tea Liquid Packet will take a placebo in the second month, after the end of the second month, do the third complete physical and mental symptom assessment (sleep habits questionnaire, anxiety questionnaire, stress questionnaire, digestive tract Symptom Questionnaire, Irritable Bowel Disorder Questionnaire), the test is completed.

Research flow chart

3. Questionnaire

The questionnaire items included sleep habits questionnaire, anxiety questionnaire, stress questionnaire, gastrointestinal symptoms questionnaire, and irritable bowel syndrome questionnaire. The details of the questionnaire are attached.

4. Collection, preservation, transportation and DNA extraction of feces

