	d3- L -Methionine (d3- L -Met) (IS2)	153.1	ESI Positive
	d9-Trimethylamine N -oxide (d9-TMAO) (IS3)	85.0	ESI Positive

7. Jing Si Herbal Tea Liquid Packet

In this experiment, Jing Si Herbal Tea Liquid Packet was used. Its ingredients are eight kinds of native Taiwan species, such as mugwort leaves, hinoki, *Ophiopogon japonicus*, *Houttuynia cordata*, bellflower, licorice, perilla leaves, and chrysanthemum. , Dampness-clearing and heat-clearing herbs, take Jing Si Herbal Tea Liquid Packet 15 ml once a day in the morning and evening.

8. Statistical Analysis

Continuous variables were expressed as mean and standard deviation if they were normally distributed; if they were not normally distributed, they were expressed as median and interquartile range. The treatment effect is presented by the improvement percentage of the sleep habits questionnaire, depression questionnaire, anxiety questionnaire, stress questionnaire, gastrointestinal symptoms questionnaire, and irritable bowel syndrome questionnaire before and after treatment, and the curative effect of Jingsi Bencao Drink Concentrate and placebo is expressed as the chi-square by the improvement percentage Chi-squared test comparison, P value less than 0.05 was considered statistically significant difference, the statistical analysis software used was SPSS 19 for Windows (SPSS, Inc, Chicago, IL, USA).

9. Sample Size Estimation

According to our ongoing research, it is estimated that the efficacy of Jing Si Herbal Tea Liquid Packet for functional dyspepsia (FD) is 75%, while the efficacy of placebo is 33.3%. It is estimated by α -error 0.05; β -error 0.20, at least 100 subjects are required to be admitted, and taking into account that the subjects may withdraw and fail to complete the trial successfully, the estimated number of subjects admitted in this study is 150.

10. Possible difficulties and solutions

Possible difficulties: According to our current research, the effect of placebo on functional dyspepsia (FD) can reach 33.3%, so if the investigators want to prove that Jing Si Herbal Tea Liquid Packet has a positive effect on patients with new coronary pneumonia three months after infection Gut-brain axis dysregulation (DGBI) had to be statistically significantly greater than placebo to have a significant effect.

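### The design is a two-period crossover, but the only stated comparison of herbal tea with placebo is an ordinary chi-square without pairing, period or a defined month-2 reference score

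*Protocol*

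**What the plan says.** Section H.2 (Experimental process) randomises subjects to herbal tea or placebo for month 1 and then switches everyone: "The original placebo will take Jing Si Herbal Tea Liquid Packet in the second month", while those "previously taking Jing Si Herbal Tea Liquid Packet will take a placebo in the second month". Symptoms are assessed before treatment, at the end of month 1, and again: "after the end of the second month, do the third complete physical and mental symptom assessment". The budget table agrees that each person takes both products. It lists "Jingsi herbal drink concentrate (2 packs*30 days*150 people") and a matching line for placebo.

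Section H.8 (Statistical Analysis) defines the treatment effect as improvement on each questionnaire, ending with the "and irritable bowel syndrome questionnaire before and after treatment". It then names one test of herbal tea against placebo: "the curative effect of Jingsi Bencao Drink Concentrate and placebo is expressed as the chi-square by the improvement percentage Chi-squared test comparison". The criterion is "P value less than 0.05 was considered statistically significant difference". H.8 does not mention pairing, period or sequence, does not restrict the test to month 1, and does not say which assessment is the 'before' score for month 2. Section H.9 works from two response rates, 75% and 33.3%, and does not refer to the crossover.

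**The concern.** An ordinary chi-squared test compares two independent groups. In this design the herbal and placebo results come from the same people. If both months enter the test, each person is counted as two, and the variance is wrong unless a person's two results are uncorrelated. The test also has no period term, so a change over time that affects both products, such as natural recovery, feeds into the comparison when the two sequences end up unequal in size.

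The undefined month-2 'before' score makes this worse, because it decides the sign of the within-subject correlation and so whether the test is too strict or too lenient. Left open, it can be settled after the data are seen.

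This is the only stated test of the product against placebo, and section H.10 rests the claim of benefit on a statistically significant advantage over placebo.

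**Working it through.** **Figures in the plan.** The protocol gives no error rate for the crossover comparison, so there is none to reproduce. The related figure is H.9's minimum of 100 subjects. A plain two-arm calculation at 75% vs 33.3%, two-sided 5% and 80% power gives 22 per arm (44 in total), so the stated inputs alone do not yield 100. The point here does not depend on that number; N = 100 is used only as the size of the simulated trial.

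**Inputs.** From the protocol: two periods, three assessments, significance level 0.05 (taken as two-sided), response rates 75% and 33.3%. Assumed, because the protocol gives nothing: the correlation structure, any period effect and the split between sequences.

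**Step 1: effect of ignoring the pairing.** Let p be the response rate under no treatment effect and phi the correlation between one person's two responses. With N people and no period effect:

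- variance assumed by the chi-square: 2p(1 − p)/N
- actual variance: 2p(1 − p)(1 − phi)/N
- true size = 2 × [1 − Φ(1.96/√(1 − phi))]

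This equals 5% only at phi = 0.

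**Step 2: the reference score sets the sign of phi.** Take three scores S0, S1, S2 with equal variance and common correlation r (assumption).

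- Both months against entry: the improvements are S0 − S1 and S0 − S2. Their covariance is proportional to 1 − r and each variance to 2(1 − r), so the correlation is +0.5.
- Each month against the preceding visit: S0 − S1 and S1 − S2. The covariance is proportional to −(1 − r), so the correlation is −0.5.

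The value of r cancels. Converting to binary responses with a bivariate normal gives:

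| Response rate | Month-2 reference | P(respond in both months) | phi | True size |
|---|---|---|---|---|
| 1/3 | entry | 0.183 | +0.323 | 1.72% |
| 1/3 | preceding visit | 0.047 | −0.290 | 8.44% |
| 1/2 | entry | 1/3 | +0.333 | 1.64% |
| 1/2 | preceding visit | 1/6 | −0.333 | 8.96% |

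First row worked through: phi = (0.183 − 1/9)/(2/9) = 0.323; √(1 − 0.323) = 0.823; 1.96/0.823 = 2.38; two-sided tail 1.72%.

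**Step 3: simulation check.** With N = 100, rate 1/3 and 80,000 runs, the ordinary chi-square rejects in 1.9% (entry) and 8.5% (preceding visit). The Mainland-Gart test, which is paired and adjusts for period, rejects in 5.5% and 5.2%. A chi-square on month 1 alone rejects in 5.0% and 4.9%. A separate simulation with a different score model (responder = 20% drop, intraclass correlation 0.3 to 0.7) gave the same directions: 2.3% to 2.5% against entry and 6.9% to 7.8% against the preceding visit.

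**Step 4: period effect.** Assume response is 20 points higher in month 2 and completers split 60/40 by sequence. With no true effect the pooled difference is 0.20 × (40 − 60)/100 = −4 points. The chi-square's size is then about 5% (entry) or 13% (preceding visit), while Mainland-Gart stays at about 5%.

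**Step 5: power.** A month-1 chi-square at 75% vs 33.3% with 50 per group has 99.3% power. At the protocol's own effect the issue is validity, not power. At a smaller assumed effect (50% vs 33.3%, N = 100) pooling does cost power: 70% against 76% for a period-adjusted paired test at latent correlation 0.3, and 73% against 87% at 0.6.

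**The case against.** The strongest reply is that H.8 never says the two months are pooled. H.2 places the laboratory tests and their before-and-after analysis at the end of month 1, and H.9 uses two plain response rates, so a month-1 comparison is a plausible reading, and there the chi-square is valid. H.2 also uses the before-treatment label for the entry assessment, which favours entry as the reference; under that reading the model gives a conservative test (1.7%). The inflated figures all need the other reference. The 60/40 split is also selected: under simple randomisation of 100 people, a split at least that uneven has probability about 5.7%, before any dropout. Finally, McNemar and Mainland-Gart statistics are themselves chi-squares.

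Much of this stands as a limit. The error is conditional on using both months, its direction depends on an undefined reference, and the correlations and period effects are assumptions. With balanced sequences, a missing period term alone does not inflate the error; it tends to make the test conservative. The size near 5% in the entry case of step 4 arises because conservatism and bias offset each other, and is not evidence that the test is sound.

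It does not remove the point. Nothing in H.8 restricts the test to month 1 or suggests a paired or period-adjusted form. A size of 1.7% is also not the stated 5%. If month 1 is what was meant, the switch and the third assessment serve no stated comparison. Nor is this detail left to a later analysis plan: the protocol names the test, and the named test does not fit the design it describes.

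**Conclusion.** The concern holds. H.2 fixes a two-period crossover, and H.8 fixes a test for independent groups as its only comparison of the products. On two-month data the nominal 5% test has a true size of roughly 1.6% to 9.0% in the equal-correlation model, depending on which visit is the month-2 reference, and about 13% if a 20-point period effect meets a 60/40 sequence split under the preceding-visit reference. These sizes rest on the assumptions stated with them; the mismatch between design and test does not. On month-1 data alone the test is valid and well powered at the protocol's assumed rates, but that restriction is not stated. Because this is the sole basis for the claim over placebo and the remedy is cheap, it should be corrected before the data are analysed.

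**What to change.** Amend section H.8 as follows:

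1. For any comparison using both months, replace the ordinary chi-square with a paired analysis that includes period: Mainland-Gart or conditional/mixed logistic regression for responder proportions, or a mixed model on questionnaire scores with treatment, period, sequence and a random subject effect. McNemar alone is not enough: in simulations with a period effect (50% in one month, 20% in the other) and a 60/40 split, its size was 10% to 13%.
2. State which assessment is the 'before' score for month 2. If a responder analysis is kept, state the responder definition it uses.
3. Keep the ordinary chi-square only for a month-1 between-group comparison, labelled as such.
4. Name one of the two as the main comparison. H.2 describes no washout, and the crossover methods assume no differential carryover, so the month-1 comparison is the one free of carryover.

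The cost is analysis wording only: no new data, visits or subjects. At 75% vs 33.3%, paired tests with 100 subjects have power of about 100%, so no larger sample is needed.

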Jing Si Herbal Tea Liquid Packet

The ingredients of Jing Si Herbal Tea Liquid Packet are mugwort leaves, houttuynia cordata, Ophiopogon japonicus, Houttuynia cordata, Campanulaceae, licorice, perilla leaves, chrysanthemum and other eight native Taiwanese herbs that can clear away moisture, dispel cold, relieve lungs and resolve phlegm, and clear away dampness and heat. Chinese medicinal herb, current research has found that it can block the combination of the new coronavirus and cells, and can also reduce cell penetration and block the virus from penetrating cells, while targeting wild-type and mutant viruses D614G, B.1.1.7, 501Y.V2 Carrying out animal studies, it was found that Jing Si Herbal Tea Liquid Packet can reduce the ability of 60 to 70% of the virus to infect the upper respiratory tract, lung, heart, and intestine of mice and reduce the expression of FKBP51, a protein related to depression, by 40%. The effect of using Jing Si Herbal Tea Liquid Packet to help reduce the amount of virus and systemic anti-inflammatory effect in patients with COVID-19. (9) In our

Version date : (Version 3, 11/10/2022)

ongoing clinical study, for functional dyspepsia (FD) patients, Jing Si Herbal Tea Liquid Packet can improve symptoms in 75% of patients, compared with only 33% of placebo.

Purpose

A double-blind randomized trial was conducted to investigate the improvement of Jingsi Bencao decoction concentrate on the physical and mental symptoms of gut-brain axis disorder (DGBI) and the changes in intestinal flora after COVID-19.

Importance

Gut-brain axis disorders (DGBI), including functional dyspepsia and irritable bowel syndrome, are gastrointestinal problems after COVID-19 infection. They are also diseases that are worthy of improvement in the efficacy of traditional Western medicine. The discovery that Jingsi Bencao Drink Concentrate improves gastrointestinal function and depression after infection with the new coronavirus can be used to improve the physical and mental symptoms of gut-brain axis disorder (DGBI).

※If there are not enough fields, please copy by yourself.

H. Research methods, steps and implementation progress

1. Please describe in detail the research methods and reasons used in this project.
2. Estimated possible difficulties and solutions.
3. If it is a continuous plan, the research progress report or primary data of the previous year should be attached at the same time.
4. Please write in Chinese format.

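### Section H.9's minimum of 100 subjects does not follow from 75% vs 33.3% at 80% power (44 to 52 between groups, 17 to 39 paired), and the rates are for FD only

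*Protocol*

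**What the plan says.** Protocol Section H.9 (Sample Size Estimation) gives four inputs: two response rates, alpha 0.05 and beta 0.20. The rates are introduced with "estimated that the efficacy of Jing Si Herbal Tea Liquid Packet for functional dyspepsia (FD) is 75%, while the efficacy of placebo is 33.3" percent. From these it concludes that "at least 100 subjects are required to be admitted". A separate, later step raises the number to 150 for withdrawals, so drop-out is not part of the 100.

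The background section on the product gives the source of the rates, an ongoing study: "for functional dyspepsia (FD) patients, Jing Si Herbal Tea Liquid Packet can improve symptoms in 75% of patients, compared with only 33% of placebo". No rate for IBS appears anywhere.

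Section H.8 (Statistical Analysis) names the test: the effect of drink and placebo is "expressed as the chi-square by the improvement percentage Chi-squared test comparison". It gives no period and no pairing.

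Section H.2 (Experimental process) describes a two-period cross-over. After month 1 the investigators "then conduct a cross-test. The original placebo will take Jing Si Herbal Tea Liquid Packet in the second month", and the other group moves to placebo. The budget agrees, since product and placebo are each costed for all 150 people ("Placebo (2 packs*30 days*150 people"). The sample is described as "including 75 subjects with functional dyspepsia (FD) and 75 subjects with irritable bowel syndrome (IBS) subjects". Section H.10 states the claim for the combined condition: "Gut-brain axis dysregulation (DGBI) had to be statistically significantly greater than placebo".

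**The concern.** A difference of about 42 percentage points is large, and 80% power to detect it should take far fewer than 100 subjects. If the stated number and the stated power do not belong together, a reader cannot tell what the trial was sized for: a pooled comparison at much higher power, a paired comparison, or two separate comparisons by diagnosis. Each carries a different power and a different assumption about IBS. The IBS assumption matters most, because half the subjects have a condition for which no response rate is given.

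**Working it through.** **Inputs.** From Section H.9: p1 = 0.75, p2 = 0.333 (taken as 1/3), alpha 0.05, power 0.80. Not stated and assumed here: two-sided test, 1:1 allocation.

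**Attempt to reproduce the 100, between groups at the end of month 1.** The mean rate is (0.75 + 0.3333)/2 = 0.5417 and the difference is 0.4167.

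n per arm = [1.96 × √(2 × 0.5417 × 0.4583) + 0.8416 × √(0.75 × 0.25 + 0.3333 × 0.6667)]² / 0.4167²
= (1.381 + 0.539)² / 0.1736 = 21.23, so 22 per arm and **44 in total**.

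With the Fleiss continuity correction, n = (21.23/4) × [1 + √(1 + 4/(21.23 × 0.4167))]² = 25.81, so 26 per arm and **52 in total**.

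Other conventions for a single comparison at 80% power do not reach 100 either:

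| Variant | Total (continuity-corrected) |
|---|---|
| One-sided | 34 (44) |
| Unpooled variance | 38 |
| Arcsine | 44 |
| Fisher or Yates, exact power | 50 |
| 2:1 allocation | 48 (57 to 60) |
| 3:1 allocation | 56 (68) |
| Bonferroni over the six questionnaires in H.8 | 68 (76) |

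**Attempt to reproduce the 100, paired over both months.** This uses McNemar's test and assumes no period or carry-over effect. Let p11 be the proportion responding on both products, b = p1 − p11 and c = p2 − p11. Then

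n = [1.96 × √(b + c) + 0.8416 × √(b + c − (b − c)²)]² / (b − c)².

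With within-subject correlation φ, p11 = p1·p2 + φ × 0.2041. The two rates allow φ only from −0.816 to 0.408.

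| φ | b | c | n | Subjects |
|---|---|---|---|---|
| −0.816 | 0.667 | 0.250 | 39.0 | **39** |
| 0 | 0.500 | 0.083 | 23.9 | **24** |
| 0.408 | 0.417 | 0 | 16.3 | **17** |

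Bonferroni over six questionnaires gives 61, 38 and 26.

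**Power that 100 evaluable subjects give.** At 50 per arm and 75% vs 33.3%, between-group power is 99.3% by the normal approximation, 99.3% exact for the uncorrected chi-squared test, and 98.7% exact with Yates correction. Paired power with 100 subjects is 99.6% at φ = −0.816 and above 99.99% at φ = 0. At 80% power, 50 per arm would detect about 61% vs 33.3% by the normal approximation. The exact corrected test reaches 78.9% power at 62% and 80.4% at 62.5%.

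**Sizing the two diagnoses separately.** With IBS rates set equal to the FD rates, closed-form sizing gives 4 × 22 = 88, or 4 × 26 = 104 corrected. Exact Fisher/Yates power is 79.0% at 24 per arm and 82.0% at 25 per arm (86.4% by the uncorrected normal approximation), so 4 × 25 = 100.

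**What the missing IBS rate could do.** The IBS rates below are assumptions, chosen only to show the range. The comparison is pooled, in month 1, at 50 per arm, half FD and half IBS, with placebo 33.3% and FD active 75%.

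| IBS active | Pooled active | Exact power, uncorrected | Exact power, corrected |
|---|---|---|---|
| 75% | 75.0% | 99% | 99% |
| 60% | 67.5% | 94% | 92% |
| 50% | 62.5% | 86% | 80% |
| 33.3% | 54.2% | 58% | 50% |

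**The case against.** The strongest defence is that 100 was obtained by sizing each diagnosis separately. An exact test first reaches 80% power at 25 per arm, and 25 × 2 arms × 2 diagnoses is exactly 100. Recruitment of 75 per diagnosis then equals 50 evaluable plus a one-third loss (50/(1 − 1/3) = 75). This arithmetic is right and fits the 75/75 split. But it remains an inference. Section H.9 mentions no sizing by diagnosis, Section H.8 describes no test by diagnosis, and the usual chi-squared formulas give 88 or 104 on this route. It also depends on IBS rates equal to the FD rates, which is never stated, so if this was the intention the text omits its key assumption.

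It can also be said that the 100 is a floor, that over-sizing does no harm at the stated rates, and that the choice of primary comparison may be left to the SAP. The absence of harm at the FD rates is conceded. It does not make the statement correct, because the sentence presents 100 as what those error rates require. The number and its inputs are printed together in the protocol, so the mismatch is not a detail deferred to the SAP.

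Two limits on the figures are fair. The upper paired size of 39 requires an extreme negative correlation, and the Bonferroni sizes answer an adjustment the protocol does not propose. Both are shown only because even they fall short of 100.

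**Conclusion.** The concern holds. Under none of the herbal-versus-placebo comparisons the protocol describes do the stated inputs lead to 100. The stated minimum is about twice the between-group requirement (44, or 52 corrected) and at least 2.5 times the paired requirement (17 to 39). The power at 100 is about 99% or higher rather than 80%. These results assume two-sided testing, 1:1 allocation and, for the paired sizes, no period or carry-over effect.

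At the FD rates the error is over-sizing. What lacks support is the 80% power for a sample that is half IBS. On the illustrative rates above, pooled power stays at 80% or more down to an IBS active rate of 50%, and falls to 50 to 58% if the drink has no effect in IBS. The trial therefore cannot be called underpowered, but its stated power has no basis for the IBS half. This should be corrected; it does not call for a change in enrolment.

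**What to change.** Keep 150 enrolled and rewrite Section H.9 to name the comparison, whether it is paired, whether the number applies per diagnosis, and the power that results. Depending on which was meant:

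- **Pooled, between groups, month 1:** state 44 (52 corrected) for 80% power, and that 100 evaluable subjects give about 99% power for 75% vs 33.3%, or 80% power for about 61% vs 33.3%.
- **Paired cross-over:** state the within-subject assumption and the size it gives (24 at zero correlation, 17 to 39 over the admissible range), and that 100 evaluable subjects give over 99% power.
- **FD and IBS sized separately:** say so, give 25 per arm per diagnosis with its power (82% exact corrected, about 86% by the uncorrected normal approximation), and state that the IBS rates are assumed equal to the FD rates.

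In every case, say that the assumed rates come from FD patients only. The cost is a text edit to one section, and enrolment and allocation stay as they are. The price is that the quoted power changes and the IBS assumption becomes visible.
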